3.2 Rationale for Study Design and Control Group

In the US, ospemifene 60 mg is the approved dose for the treatment of dyspareunia, a symptom of VVA. In a prior study (Study 15-50310), this dose demonstrated efficacy in the treatment of vaginal dryness due to menopause. Therefore, subjects in the treatment group of this study will receive ospemifene 60 mg QD.

For this study, placebo has been chosen as the comparator since there is no other oral non-hormonal therapy approved for treatment of vaginal dryness due to postmenopausal VVA; the current clinical standard of care is non-hormonal lubricants. Subjects in this study will be provided with K-Y Jelly® to be used as needed for treatment of vaginal dryness. The 12 week treatment duration is following the regulatory guidance for treatment of symptoms of VVA due to menopause.

3.3 Study Duration

3.3.1 Study Duration in Individual Subjects

Subjects may be participating in the study for up to 18 weeks.

3.3.2 Planned Duration for the Study

The study is expected to require approximately 60 weeks for enrollment of subjects and 14 weeks after the last subject is randomized for a total study duration of approximately 74 weeks.

4. STUDY POPULATION SELECTION

4.1 Study Population

The study population will consist of approximately 600 female subjects aged ≥ 40 and ≤ 80 years who have moderate to severe vaginal dryness, as self-reported MBS of VVA due to menopause. Those who meet the following eligibility criteria may be randomized.

4.2 Inclusion Criteria

Subjects must meet all of the following inclusion criteria to be eligible to participate in the study:

AT VISIT 1 - SCREENING VISIT:

1. Subject understands the study procedures and risks and voluntarily agrees to participate by giving written informed consent.
2. Subject is ≥ 40 and ≤ 80 years old at time of signing informed consent.
3. Subject is a postmenopausal woman as defined by one of the following:
 - a. Is ≥ 45 years old; her last spontaneous menstrual bleeding must have been ≥ 12 months prior to screening
 - b. Is ≥ 45 years old; she does not remember the date of her last spontaneous menstrual bleeding and has follicle-stimulating hormone (FSH) levels >40 IU/L
 - c. Has had a hysterectomy **WITHOUT** oophorectomy and serum FSH levels >40 IU/L
 - d. Has had a bilateral oophorectomy at least 6 weeks prior to screening
4. The subject has 5% or fewer superficial cells in the maturation index of the vaginal smear.
5. Subject has vaginal pH >5.0 .
6. Subject has moderate to severe vaginal dryness as the self-reported MBS of VVA.

AT VISIT 2 - RANDOMIZATION:

7. Subject has an intact uterus with double layer endometrial thickness <4 mm at screening, as determined by a centrally-read ultrasound **OR** had a hysterectomy.
8. Subject has an intact uterus and has no evidence of hyperplasia, cancer, or other pathology in an endometrial biopsy **OR** had a hysterectomy.
9. Subject has a negative screening mammogram (obtained at screening or within 9 months prior to screening) and a normal clinical breast examination at screening.

Note: Mammograms obtained within 9 months of screening must be available.

10. Subject has $\leq 5\%$ superficial cells in the maturation index of the vaginal smear at screening (results will be from Visit 1).

11. Subject has vaginal pH >5.0.
12. Subject has moderate to severe vaginal dryness as the self-reported MBS of VVA.

4.3 Exclusion Criteria

Subjects who meet any of the following exclusion criteria are not eligible to participate in the study:

AT VISIT 1 - SCREENING VISIT:

1. Subject has clinically significant abnormal findings in the physical examination.
2. Subject has a body mass index (BMI) equal to or greater than 38 Kg/m².
3. Subject has uncontrolled hypertension (systolic blood pressure [BP] \geq 140 mmHg or diastolic BP \geq 90 mmHg on two measurements at least 5 minutes apart).
4. Subject has clinically significant abnormal findings in the gynecological examination other than signs of vaginal atrophy (eg, uterine or vaginal prolapse \geq Grade 2).
5. Subject has uterine/vaginal bleeding of unknown origin.
6. Subject has a vaginal infection and refuses treatment, or the infection doesn't respond to the treatment.
7. Subject has taken any of the following hormonal medications:
 - a. Vaginal hormonal products (rings, creams, gels) within 14 days prior to screening,
 - b. Oral or transdermal estrogen and/or progestin therapy within 60 days prior to screening,
 - c. Intrauterine progestin therapy within 60 days prior to screening,
 - d. Progestin implants or estrogen-alone injectable drug therapy within 90 days prior to screening, or
 - e. Estrogen pellet therapy or progestin injectable drug therapy within 6 months prior to screening.
 - f. Other sex hormones or medications that are expected to clinically significantly affect sex hormone levels within 60 days prior to screening
8. Subject has taken a SERM (raloxifene, tamoxifen, toremifene, or clomiphene), tibolone, or any other medication that is expected to have clinically-significant estrogenic and/or antiestrogenic effects within 60 days prior to screening.
9. Subject has regularly used any dietary supplement or herbal therapy, including black cohosh, soy (including soy milk), phytoestrogens, or over the counter agents known to possibly have estrogenic vaginal effects within 30 days prior to screening.
10. Subject is currently using any of the other prohibited medications listed in Protocol Section 6.2.1 Prohibited Therapy.
11. Subject consumes >14 alcoholic drinks per week. (One drink= 1.5 oz of distilled spirits, 12 oz of beer, or 5 oz of wine).

12. Subject is suspected of having or confirmed to have a malignancy or has history of malignancy within 10 years prior to screening (Except for non-melanoma skin cancer or carcinoma in situ of the cervix). Women with a history of breast cancer in remission for >10 years and not taking any adjuvant therapy are eligible to participate.
13. Subject has any history of thromboembolic or blood coagulation disorders.
14. Subject has any history of cerebrovascular accident (eg, bleeding, stroke, or transient ischemic attack [TIA]) or cardiac ischemic disorder (eg, myocardial infarction, unstable angina).
15. Subject participated in another clinical study within 30 days prior to screening.
16. Subject has any physical or mental condition which, in the opinion of the Investigator, may interfere with the subject's ability to comply with the study procedures.
17. Subject has previously taken ospemifene as a treatment.
18. Subject has any condition or situation which, in the opinion of the Investigator, might pose a risk to the subject or interfere with participation in the study.
19. Subject has an abnormal Papanicolaou (PAP) test result at screening with any of the following findings according to the Bethesda System (2001) Classifications:
 - a. Atypical Squamous Cells of Undetermined Significance (ASCUS) (human papilloma virus [HPV] High Risk Positive),
 - b. Atypical Squamous Cells - cannot exclude high-grade squamous intraepithelial lesion (HSIL),
 - c. Atypical Glandular Cells (Endocervical, Endometrial, not otherwise specified [NOS]),
 - d. Low Grade squamous intraepithelial lesion (SIL),
 - e. High Grade SIL,
 - f. Carcinoma, or
 - g. Unsatisfactory specimen (one retest will be allowed).
20. Subject has uterine polyps.
21. Subject has symptomatic and/or large uterine fibroids (estimated size >3 cm).
22. Subject has clinically significant abnormalities on electrocardiogram (ECG).
23. Subject has clinically significant abnormalities in any safety laboratory tests.
24. Subject has liver enzyme levels (alanine aminotransferase [ALT], aspartate aminotransferase [AST]) > 3 times the upper limit of normal (ULN).
25. Subject is heterozygous or homozygous for Factor V Leiden.
26. Subject has moderate to severe renal impairment (estimated glomerular filtration rate [eGFR] based on Modification of Diet in Renal Disease [MDRD equation] < 60 mL/min/1.73 m³).
27. Subject has a history of hepatic impairment (including chronic hepatitis C, hepatitis B, Child-Pugh class B, or Child-Pugh class C).

AT VISIT 2 – RANDOMIZATION:

28. Subject has any condition or situation which, in the opinion of the Investigator, might pose a risk to the subject or interfere with participation in the study.

4.4 Screen Failures

Screen failures are defined as patients who consent to participate in the study but are not subsequently randomized to the study drug. Minimal information collected will include informed consent date, baseline subject characteristics, all of the eligibility criteria not met, reasons for screen failure, adverse events (AEs) that led to screen failure, and any serious adverse events (SAEs); these will be entered in the electronic case report form (eCRF).

5. STUDY TREATMENT(S)

5.1 Description of Treatment(s)

Study treatment will be ospemifene 60 mg or matching placebo taken once daily with food.

5.1.1 Test Drug

Ospemifene will be provided as a white to off-white, oval, film-coated, biconvex tablet with one side engraved with “60.” Test drug will be manufactured by:

CPI

5.1.2 Placebo

Placebo will be provided as a white to off-white, oval, film-coated, biconvex tablet with one side engraved with “60,” which will match the test drug. Placebo will be manufactured by:

CPI

5.2 Treatments to be Administered

Each subject who qualifies for entry into the study will be randomized to 1 of 2 treatment groups. Subjects will be instructed to take one tablet of either ospemifene 60 mg or matching placebo, orally, once a day with food for 12 weeks (Treatment Period).

5.3 Selection and Timing of Dose for Each Subject

Subjects will be randomly assigned to either ospemifene or placebo for the 12-week duration of the treatment period.

Study drug should always be taken with food. Study subjects will be instructed to identify the most appropriate time for dosing each day (ie, time of day most likely to be associated with highest compliance and convenience). After the time of dosing is established, every effort should be made to take study medication at approximately the same time each day. To assess exposure, dates in which the subject took study drug will be captured in the eCRF.

5.4 Method of Assigning Subjects to Treatment Groups

At screening, the interactive web or voice response system (IxRS) will be used to assign each subject with an ID number that will be used to identify a subject in all data systems.

At randomization, study drug treatment, ospemifene 60 mg or matching placebo, will be assigned in a 1:1 ratio using IxRS according to the randomization schedule. Randomization will be stratified by the subject's severity of vaginal dryness (moderate or severe) and the presence or absence of a uterus, such that both treatment groups will have similar proportions of subjects with moderate or severe vaginal dryness and with or without a uterus at the start of the study.

5.5 IxRS Blinding and Unblinding

This study will be conducted in a double-blind manner using a placebo matching the test drug in appearance, labeling, and packaging. All subjects, the Investigator, all study personnel, and the Sponsor will be blinded to the treatment assigned at randomization until database lock. Following database lock, the Sponsor will be unblinded to the randomization codes.

The randomization schedule will be maintained by the IxRS in a blinded manner and will not be accessible to anyone until unblinding, except for the Sponsor's drug supply management staff, IxRS clinical coordinator(s), and IxRS vendor staff.

Emergency unblinding of the study drug should only be undertaken when it is critical to the safety and effective medical treatment of a subject. Prior to unblinding, and if the situation allows it, the Investigator should try to contact the Sponsor's medical monitor in order to obtain additional information about the study drug. The Investigator will contact the IxRS to provide the subject's study identification information and confirm the necessity for unblinding. The Investigator will subsequently be provided with the subject's assigned drug treatment as well as a confidential fax or e-mail confirming this information. The system will automatically inform the medical monitor, site monitor, Clinical Trial Manager (CTM), drug safety, and the Sponsor that a randomization code has been broken.

If the blind is broken for any study subject for whatever reason, the Investigator must document the Subject ID, date and time of breaking the blind, and must clearly explain the reasons for breaking the code, and document this in the eCRF.

The blind will be broken by designated Drug Safety personnel for an individual subject for purposes of submitting a suspected unexpected serious adverse reaction (SUSAR) or an expedited report to health authorities based on regulatory requirements.

Once a subject is unblinded, she is no longer eligible to receive the study drug treatment and must be discontinued from the study and follow-up assessments must be completed.

5.6 Packaging and Labeling

Study drug will be packaged in bottles that will be provided to the subject at Visits 2, 3, and 4. Each bottle will contain 35 tablets. Throughout the study the same size bottle will be used and will be labeled in English with a label that specifies the Sponsor, the study number, bottle identification number (BIN), number of tablets, cautionary statement, and storage conditions.

After randomization, at Visits 2, 3, and 4, each subject will receive adequate drug supply to take home; this supply will be sufficient to provide the study drug until the next clinic visit. Regardless of randomization assignment, all subjects will be required to take 1 tablet of study drug every day during the treatment period.

The Sponsor or designee will provide the Investigator with adequate quantities of the study drug. The site pharmacist or medically qualified staff member will dispense the study drug to each subject as described in Sections 5.2, 5.3 and 5.7.

5.7 Storage and Accountability

Bottles of study drug (ospemifene and placebo) should be stored at 20°C to 25°C (68°F to 77°F); excursions permitted to 15°C to 30°C (59°F to 86°F) and under secure conditions.

A qualified person at the study site must be designated to receive, handle, and store the study drug. The Investigator (or designee) will maintain an accurate record of the receipt of the study drug as shipped by the Sponsor (or designee). One copy of this receipt will be returned to the Sponsor (or designee) when the contents of the study drug shipment have been verified.

Upon receipt, all study drugs should be stored safely, properly, and securely in compliance with the specified instructions. Only the Investigator and authorized associates should have access to the study drug.

The Investigator or qualified member of the study team must maintain an accurate record of the study drug dispensed to and returned by the subjects. Subjects will be asked to return all unused study drug and empty bottles at required study visits, at the end of the study, or at the time of study drug discontinuation.

At completion of the study, a final reconciliation of all study drugs will be performed and all unused study drug and empty bottles will be returned or disposed of as instructed by the Sponsor (or designee).

Drug accountability records will be available for verification by the designated monitors at each monitoring visit. The study drug must not be used for any purpose other than for this study.

5.8 Investigational Product Retention at Study Site

No study drug will be retained at the study site in this study.

5.9 Treatment Compliance

The Investigator and/or study personnel will assess treatment compliance at each visit using pill counts and information provided by the subject. The Investigator should stress to the subject the importance of compliance and ensure that she understands the dosing instructions. Compliance checks by tablet count will be performed by qualified site

personnel in order to verify that the correct number of doses have been taken based on the actual number of days that have elapsed between designated clinic visits.

A record of the study drug taken by the subject will be made in the eCRF as required. In the event of discrepancy between the tablet count and the information provided by the subject, the information provided by the subject will be recorded in the eCRF.

Based on compliance checks, a subject will be counseled by the site about the importance of taking the study drug as directed if < 100% of the required study drug has been taken by that subject. If compliance issues persist and overall dosing compliance is < 80%, the Investigator may consider discontinuing the subject from the study.

In the event a subject has interrupted or discontinued study drug, the subject must inform the Investigator and the rationale must be provided in the source document. The subject may continue in the study after agreement with the Investigator. If the study drug has been temporarily discontinued for safety reasons, the Investigator must document the reasons in the source document and discuss with the medical monitor prior to the subject reinitiating study drug. All interruptions of study drug (≥ 1 day) should be captured in the eCRF.

In the event a subject is withdrawn for compliance reasons (eg, missed doses or visits), the Investigator will notify the Sponsor or designee promptly and will make every effort to complete the early termination assessments and the Completion/Discontinuation eCRF. The Investigator must register all subject discontinuations in the IxRS.

6. RESTRICTIONS

6.1 Prior Therapy

Prior therapies are defined as therapies which were taken prior to the initiation of study treatment.

Any prior therapy (prescription drugs, over-the-counter [OTC] drugs, herbal supplements, procedures without any medication) taken by the subject within 6 months prior to screening will be recorded in the eCRF and the information will include the name of the medication/procedure, administration route of drug(s), duration of treatment, and reason for use.

6.2 Concomitant Therapy

For randomized subjects, all medications taken (prescription and OTC) and all procedures performed after Randomization and through the end of the study, including the 2-week follow up call, will be recorded in the eCRF. The information will include the medication/procedure, duration of treatment and the reason for it. Additionally for medications, administration route of drug(s) will be captured.

AEs requiring medication or changes to medication must be recorded on the appropriate eCRFs. Medication taken for a procedure will also be included.

6.2.1 Prohibited Therapy

Prohibited medications should not be taken by subjects at any time during the study. Use of prohibited concomitant therapy(ies) may result in study discontinuation. The following medications are prohibited:

- Dietary supplements and herbal therapies with assumed clinically significant estrogenic vaginal effects (See Appendix 1)
- Any form of local vaginal hormonal products
- Any form of oral or transdermal estrogen or progestin
- Any form of progestin implants (subdermal or intrauterine) or estrogen implants (pellets)
- Any form of estrogen-alone or progestin-alone injectable drug therapy
- Sex hormones or medications that are expected to affect clinically significant sex hormone levels
- Any SERMs
- Any vaginal lubricant or moisturizer other than that provided by the Sponsor for use in the study
- Use of systemic fluconazole, rifampicin, rifabutin, carbamazepine, phenytoin, St John's wort

Additional medications identified that may have a significant impact on the study drug or the indication studied should also be prohibited at the Investigator's discretion.

7. STUDY PROCEDURES AND METHODS OF ASSESSMENTS

7.1 Informed Consent

The Investigator or Sub-investigator will fully explain the nature of the study to the subject using the institutional review board (IRB)-approved informed consent form (ICF). When the subject agrees to participate in the study, the subject must voluntarily sign the ICF prior to the initiation of any study procedures. A copy of the signed and dated ICF will be given to the subject. The signed and dated original consent form will be retained by the Investigator. Informed consent will be obtained from all subjects. A subject cannot be entered into the study until she has signed and dated the consent form.

In the event a subject withdraws consent of vaginal imaging after signing ICF, the withdrawal will be documented on appropriate page of the already signed ICF and in the subject file. The photographs taken prior to withdrawal of consent will be used for study research purposes as described in the informed consent.

The Investigator or Sub-investigator is responsible for ensuring that the subject understands the risks and benefits of participating in the study, including answering any questions the subject may have throughout the study and sharing any new information in a timely manner that may be relevant to the subject's willingness to continue her participation in the study.

7.2 Demographics, Baseline Subject Characteristics, and Medical History

Demographic data and medical history, including current medical condition(s), will be collected at Visit 1 (Screening) and concurrent medical signs and symptoms will be reviewed prior to Visit 2 (Day 1, Randomization).

Baseline subject characteristics will be obtained and entered in the eCRF. These include date of signed informed consent, date of birth, gender, race, ethnicity, duration of VVA, severity of symptoms of VVA and identification of the most bothersome for the subject, presence or absence of a uterus, prior therapy, and medical history for the 2 years prior to screening, except for any history of cancer. Any history of cancer should be captured in the eCRF regardless of how long ago it occurred.

Medical history may include but is not limited to evaluation for past or present cardiovascular, respiratory, gastrointestinal, renal, hepatic, neurological, endocrine, metabolic, lymphatic, hematologic, immunologic, dermatologic, psychiatric, genitourinary, drug abuse, or any other diseases or disorders, surgical history, and history of diagnosis of VVA.

7.3 Enrollment in the Study and Dispensing Study Drug

At screening, after a subject signs the informed consent, the Investigator, Sub-investigator, or designee will contact the IxRS to obtain a subject ID.

At Visit 2, after a subject is determined to be eligible according to the inclusion/exclusion criteria, the Investigator, Sub-investigator, or designee will contact the IxRS to randomize the patient. After randomization of the subject, the Investigator, Sub-investigator, or site pharmacist will dispense the study drug as specified in Section 5 using the BIN provided by IxRS.

7.4 Electronic Diary (eDiary)

During the Treatment Period, subjects will document daily in an eDiary, their use of study drug, use of lubricant, and sexual intercourse. Subjects will also be asked to record overall satisfaction with treatment on a weekly basis. At Visit 2, after randomization, subject will be asked to use an eDiary and clear instructions will be provided on how to use it. Subjects will be allowed to use their own smartphone or tablet as the eDiary by downloading an application, as instructed by the site's personnel. For subjects who do not have a smartphone, an eDiary device will be provided.

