| Concomitant Therapy | | | X | X | X | X |
| Adverse Events | X ^j | X | X | X | X | X |

| Evaluation | Screening | Randomization | Treatment | | | FU ^q |
|--|--|----------------|-----------|------|----------------|-----------------|
| | V1 | V2 | V3 | V4 | V5 | TC |
| | Within 4 Weeks Prior to Day 1 ^a | Day 1 | Wk 4 | Wk 8 | Wk 12/ ET | Wk 14 |
| Cervical PAP Smear | X ^o | | | | | |
| Vaginal pH | X ^o | X ^p | X | X | X | |
| Vaginal Smear/ Maturation Index | X ^o | X ^p | X | X | X | |
| Vaginal Health Index (VHI) | | X | X | X | X | |
| Vulvar Health Index (VuHI) | | X | X | X | X | |
| Vulvo-Vaginal Imaging ^k | | X | | | X | |
| Endometrial Thickness (TVU) | X | | | | X | |
| Endometrial Histology (Biopsy) | X | | | | X ⁿ | |
| Mammogram | X ^l | | | | | |
| Dispense eDiary/Return eDiary | | X | | | X | |
| eDiary Compliance | | | X | X | X | |
| Assessment of symptoms of VVA | X ^o | X ^p | X | X | X | |
| Dispense Study Medication | | X | X | X | | |
| Dispense Lubricant | | X | X | X | | |
| Study Medication Compliance ^m | | | X | X | X | |
| Reinforce Compliance with Study Medication | | X | X | X | | |
| Study Medication Return | | | X | X | X | |
| Female Sexual Function Index (FSFI) | | X | X | X | X | |

| Evaluation | Screening | Randomization | Treatment | | | FU ^q |
|------------------------------------|--|---------------|-----------|------|--------------|-----------------|
| | V1 | V2 | V3 | V4 | V5 | TC |
| | Within 4 Weeks Prior to Day 1 ^a | Day 1 | Wk 4 | Wk 8 | Wk 12/ ET | Wk 14 |
| Urinary Distress Inventory (UDI-6) | | X | X | X | X | |

ET = Early termination; **FU** = Follow-up; **TC** = Telephone call.

- a Enough time between Visit 1 and Visit 2 should be allowed to receive the results of tests conducted as part of Visit 1, therefore, Visit 2 should not take place earlier than 1 week after Visit 1.
- b Subject ID number will be assigned through the interactive web or voice response system (IxRS).
- c Medical history should be captured for the 2 years prior to screening, except for any history of cancer which should be captured regardless of the time.

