9.2.11 Frequency of Lubricant Application and Sexual Activity

These will be recorded daily in an electronic diary (eDiary). The number of days using lubricant and having intercourses will be summarized by using the number of non-missing observations, arithmetic mean, SD, and median by week for each treatment. They will be compared among each treatment group using Welch's t-test. And the mean

values derived from data in each week will be compared using the Welch's t-test. In the summarization, subjects with no record over half days during each week will be excluded.

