	Week 8	ITT	ANCOVA	Treatment, Baseline	Secondary analysis
Change from baseline (Randomization) in bone marker	Week 12	ITT	ANCOVA	Treatment, Baseline	Secondary analysis
	Week 4	ITT	ANCOVA	Treatment, Baseline	Secondary analysis
	Week 8	ITT	ANCOVA	Treatment, Baseline	Secondary analysis
Frequency of lubricant application and sexual activity	Weekly	ITT	Welch's t-test	---	Secondary analysis
	Overall	ITT	MIMRM	Treatment, Week, Treatment*week	Secondary analysis
Overall satisfaction with treatment	Weekly	ITT	Wilcoxon rank-sum test	---	Secondary analysis

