3 Sometimes (about half the time)
2 A few times (less than half the time)
1 Almost never or never
10. Over the past 4 weeks, how **difficult** was it to maintain your lubrication ("wetness") until completion of sexual activity or intercourse?
- 0 No sexual activity
1 Extremely difficult or impossible
2 Very difficult

- 3 Difficult
- 4 Slightly difficult
- 5 Not difficult

Orgasm

11. Over the past 4 weeks, when you had sexual stimulation or intercourse, how **often** did you reach orgasm (climax)?
- 0 No sexual activity
 - 5 Almost always or always
 - 4 Most times (more than half the time)
 - 3 Sometimes (about half the time)
 - 2 A few times (less than half the time)
 - 1 Almost never or never
12. Over the past 4 weeks, when you had sexual stimulation or intercourse, how **difficult** was it for you to reach orgasm (climax)?
- 0 No sexual activity
 - 1 Extremely difficult or impossible
 - 2 Very difficult
 - 3 Difficult
 - 4 Slightly difficult
 - 5 Not difficult
13. Over the past 4 weeks, how **satisfied** were you with your ability to reach orgasm (climax) during sexual activity or intercourse?
- 0 No sexual activity
 - 5 Very satisfied
 - 4 Moderately satisfied
 - 3 About equally satisfied and dissatisfied
 - 2 Moderately dissatisfied
 - 1 Very dissatisfied

Satisfaction

14. Over the past 4 weeks, how **satisfied** have you been with the amount of emotional closeness during sexual activity between you and your partner?
- 0 No sexual activity
 - 5 Very satisfied
 - 4 Moderately satisfied
 - 3 About equally satisfied and dissatisfied
 - 2 Moderately dissatisfied
 - 1 Very dissatisfied
15. Over the past 4 weeks, how **satisfied** have you been with your sexual relationship with your partner?

- 5 Very satisfied
- 4 Moderately satisfied
- 3 About equally satisfied and dissatisfied
- 2 Moderately dissatisfied
- 1 Very dissatisfied

16. Over the past 4 weeks, how **satisfied** have you been with your overall sexual life?

- 5 Very satisfied
- 4 Moderately satisfied
- 3 About equally satisfied and dissatisfied
- 2 Moderately dissatisfied
- 1 Very dissatisfied

Pain

17. Over the past 4 weeks, how **often** did you experience discomfort or pain during vaginal penetration?

- 0 Did not attempt intercourse
- 1 Almost always or always
- 2 Most times (more than half the time)
- 3 Sometimes (about half the time)
- 4 A few times (less than half the time)
- 5 Almost never or never

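### Diary intercourse days are compared with no pre-treatment term, although FSFI Question 17 at Visit 2 already supplies a usable covariate

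*Protocol*

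**What the plan says.** Protocol 7.4 introduces the diary only once treatment has been assigned: "At Visit 2, after randomization, subject will be asked to use an eDiary". It limits recording to treatment: "During the Treatment Period, subjects will document daily in an eDiary, their use of study drug, use of lubricant, and sexual intercourse". SAP Table 2 accordingly opens its first diary window on Day 1.

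SAP 9.2.11 stands among the secondary endpoints that are tested inferentially. It defines the endpoint by day counts ("The number of days using lubricant and having intercourses will be summarized") and gives the test: "They will be compared among each treatment group using Welch's t-test". The same test is applied to the mean of the weekly values. SAP Table 5 adds an overall repeated-measures model whose terms are "Treatment, Week, Treatment*week". Neither analysis has a baseline term.

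The FSFI is scheduled at Visit 2 (Protocol Table 3.1-1). Protocol 8.2 lists it ahead of the IxRS call that randomizes the woman, and requires all baseline procedures to precede the first dose. Question 17 looks back over 4 weeks and offers the answer "Did not attempt intercourse", scored 0 in SAP Appendix 2. The SAP uses that answer only to build the FSFI scores.

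**The concern.** The primary MMRM and GEE models and every ANCOVA row of SAP Table 5 adjust for baseline. The diary counts do not, because no diary baseline exists. Sexual activity is not an entry criterion (Protocol 4.2 and 4.3) or a stratification factor (Protocol 5.4), and it is not listed in SAP Table 3. Some women may therefore have no intercourse before or during the study. Their zeros add spread that treatment does not cause and that a pre-dose answer could partly explain.

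At stake is the width of the confidence interval for the difference in intercourse days, and whether the estimate is adjusted when one arm happens to contain more inactive women.

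**Working it through.** **The plan's own figure.** The only power stated is at least 90% for the four co-primary endpoints (Protocol 9.2, SAP 4.3). For the smallest effect size, 0.27, with 300 per arm: 0.27 × √(300/2) = 3.307, and Φ(3.307 − 1.96) = 0.911. The other three effect sizes (0.70, 0.83, 0.68) give power above 99.99%, so the figure reproduces. It does not concern the diary, for which no power is given.

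**Assumptions for intercourse days** (none is in the documents): 280 evaluable women per arm; fraction q = 0.20 to 0.50 inactive at baseline; probability s = 0.85 to 0.95 of keeping the same status on study; active women average m = 1.2 days per week, with gamma spread of shape k = 1, 2 or 4; binomial day-to-day noise over 7 days; a 30% relative increase on ospemifene.

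**Formulas**, with variances in units of m²:
- Share active on study: π = (1−q)s + q(1−s)
- Variance explained by Question 17 status: N = q(1−q)(2s−1)²
- Variance between women: B = π(1+1/k) − π²
- Day-count noise: e = π[m − m²(1+1/k)/7] / (W m²), with W = 1 for one week and 12 for the 12-week mean
- R² = N/(B+e)

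**Variance explained at the two ends of the grid**

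| | q=0.20, s=0.85, k=1 | q=0.50, s=0.95, k=4 |
|---|---|---|
| π | 0.71 | 0.50 |
| N | 0.16×0.49 = 0.0784 | 0.25×0.81 = 0.2025 |
| B | 1.42−0.5041 = 0.9159 | 0.625−0.25 = 0.3750 |
| e, one week | 0.71×0.7886/1.44 = 0.3888 | 0.50×0.9429/1.44 = 0.3274 |
| R², one week | 0.0784/1.3047 = 0.060 | 0.2025/0.7024 = 0.288 |
| R², 12-week mean | 0.0784/0.9483 = 0.083 | 0.2025/0.4023 = 0.503 |

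**Lower persistence, s = 0.70.** Then (2s−1)² = 0.16.
- q = 0.20, k = 1: π = 0.62, N = 0.0256, B = 0.8556. R² is 0.0256/1.1951 = 0.021 for one week and 0.0256/0.8839 = 0.029 for the mean.
- q = 0.50, k = 4: N = 0.04. R² is 0.04/0.7024 = 0.057 for one week and 0.04/0.4023 = 0.099 for the mean.

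**Power for one week.** δ = 0.3π/√(B+e). Power ≈ Φ(δ√140 − 1.96); with the covariate, δ is divided by √(1−R²).
- Low end: δ = 0.213/1.142 = 0.1865. Power is Φ(2.207−1.96) = 0.597 unadjusted and Φ(2.276−1.96) = 0.624 adjusted, a gain of 2.7 points.
- High end: δ = 0.15/0.838 = 0.179. Power is Φ(2.118−1.96) = 0.563 unadjusted and Φ(2.510−1.96) = 0.709 adjusted, a gain of 14.6 points.

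These use the placebo-arm variance in both arms. A larger variance on ospemifene lowers both power levels, so the gain is the figure to read.

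**Chance imbalance.** With 300 per arm and a share p attempting intercourse, SE = √(2p(1−p)/300). For p = 0.5, SE = 0.0408: the 95% range is ±8.0 points and the chance of a gap of 5 points or more is 2[1−Φ(1.225)] = 22%. For p = 0.8, SE = 0.0327: ±6.4 points and 2[1−Φ(1.531)] = 13%.

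**The case against.** The strongest reply is that nothing here is an error. Allocation is random, so the Welch tests keep their type I error. A reader might infer that a baseline imbalance biases the comparison. It does not: that variability is already in the Welch standard error. This stands, and the point is one of precision and of conditioning on a known covariate.

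A reader might also carry the point over to lubricant days, which share the diary and the test. The documents do not support that. The FSFI asks nothing about applied lubricant, and Protocol 3.2 supplies it as needed for dryness, not only for intercourse. Other lubricants are prohibited after screening and study lubricant is first dispensed at Visit 2, so even a screening diary would give little comparable baseline.

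Nor should the upper figure of about 50% be read onto the weekly tests. It belongs to the 12-week mean, where day-count noise averages out. Persistence drives all the figures and is unknown: supplied lubricant or active drug could change activity. Calling Question 17 a strong predictor would go beyond the documents.

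Finally, the endpoint carries limited weight. Intercourse frequency is not in the protocol's objectives or secondary endpoint list, and the diary counts are not alone in lacking a baseline term: the responder and satisfaction rows of Table 5 have none either. This limits the importance of the change but is no reason against it.

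**Conclusion.** The point holds for intercourse days as a free improvement. The planned analysis is valid but omits a relevant pre-dose covariate that the trial already collects. On the stated assumptions, Question 17 explains about 6-29% of the variance of single-week counts, worth about 3-15 points of power for a 30% increase, and about 8-50% for the 12-week mean. If only 70% keep their status, the range is about 2-10% across both. All these sizes rest on assumed activity rates, spread and persistence. The item is a yes/no answer over 4 weeks, so it can serve as a covariate but not as a baseline for change in days. No gain is shown for lubricant days, and the co-primary results and their power do not change.

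**What to change.** Before unblinding, amend SAP 9.2.11 and Table 5 for intercourse days:
- Replace the Welch tests, weekly and on the mean of the weekly values, with ANCOVA using robust standard errors. The terms are treatment and Visit 2 FSFI Question 17 status (attempted or not attempted).
- Keep women who lack the item by giving them a missing category.
- Add the same covariate to the overall repeated-measures model in Table 5.

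For lubricant days, state that no direct baseline exists; the covariate is optional there.

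The cost is a short edit to 9.2.11 and one covariate in Table 5. No new data, visits or burden on the women are needed, and the diary schedule stays as it is.
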